In summary, cetuximab exhibits antitumor activity in advanced cases of squamous carcinoma of the skin, a population that represents a major unmet need with few proven treatment options. Our planned study will assess the ability of cetuximab to shrink locally advanced or aggressive tumors prior to surgery, measuring tumor response rate as a co-primary endpoint, and will investigate whether the delivery of this medication could possibly result in improved surgical reconstructive options. This trial will provide a unique window of opportunity to investigate the antitumor activity of cetuximab in patients with aggressive or recurrent squamous skin cancers who are candidates for neoadjuvant cetuximab. This trial will also allow us to assess the safety and feasibility of cetuximab in this patient population, which historically is of greater age and has more comorbid conditions than

patients with other advanced squamous tumors, such as locally advanced squamous tumors of the head and neck.

An important strength of this study is the use of serial biopsies to allow us to investigate the mechanism of action of cetuximab and to discover potential predictors of response and/or resistance that can be validated in future trials. Our mechanistic studies will focus on 1) apoptosis and 2) ADCC as possible mechanisms of cell death. Pre-and post-treatment tissues will be assayed for evidence of increased caspase-3 as an indication of apoptosis and for evidence of ADCC. We will also measure changes in protein or mRNA production in response to cetuximab that may lead us to discover potential mechanisms of response or resistance. For instance, as we are also investigating in protocol CINJ# 031204, there is evidence that EGFR and IGF-1R interact on multiple levels, either through a direct association between the two receptors, by mediating the availability of each others ligands, or indirectly, via common interaction partners such as G protein coupled receptors (GPCR) or downstream signaling molecules, a cross-talk that may play a role in resistance to EGFR inhibitors. We will be able to explore protein expression of EGFR and IGF1R pathway members in pre-and –post treatment tumor samples. Finally, we will utilize the FoundationOne genomic profile to assess the relationship of known DNA mutations with clinical endpoints such as clinical benefit and conversion to resectability. It is known that mutations in the TP53 tumor suppressor gene are very common in SCCs (Brash, Rudolph et al. 1991) and occur early in skin cancer development in keratinocytes (Jonason, Kunala et al. 1996, McGregor, Berkhouit et al. 1997). Inactivation of CDKN2A and activating RAS mutations have also been described (Boukamp 2005). It is not clear, however, if these events are the main drivers of tumor initiation and maintenance, or if other potentially targetable genomic gains or losses occur which may be responsible. Our analysis will provide preliminary information that may shape personalization of treatment for these patients and optimize patient selection for therapy in the future. Of great use will also be the banked tumors that will be collected and stored as part of this study, an extremely useful resource for testing alternative hypotheses as additional information becomes available.

Figure 12 From *Chen LF, Cohen E, Grandis JR. New Strategies in Head and Neck Cancer: Understanding Resistance to Epidermal Growth Factor Receptor Inhibitors. Clin Cancer Res 2010;16:2489- 2495.*

[figure not shown]

Fig. 1. EGFR signaling pathway and several mechanisms of resistance to EGFR-targeted therapies.

### 3. Participating Institutions

This protocol will be available at the Rutgers Cancer institute of New Jersey/RWJUH in New Brunswick and Hamilton Campuses. All biopsies and subsequent surgery will be performed at these facilities.

### 4. Experimental Design and Methods

#### 4.1 Duration of Study

20 patients are planned to be enrolled. The patients will be under active treatment with cetuximab monotherapy for approximately 8 weeks. Afterwards, they will be assessed for disease response and determination of whether the lesion is potentially resectable will be made. We expect that patients will be accrued within 24 months and that followup time will average 18-24 months per patient.

### 5. Patient Selection Criteria

#### 5.1 Inclusion Criteria

A patient is eligible for enrollment if all of the following inclusion criteria are met.

5.1.1 Patients must have untreated or relapsed SCCS that is considered to be aggressive and locally advanced by the following criteria: tumors 2 cm or more, tumors invading deep tissues such as muscle, cartilage or bone; tumors showing perineural invasion, and/or tumors metastatic to loco-regional lymph nodes. Patients may have had prior surgical interventions or been treated with investigational agents with residual or recurrent disease.

5.1.2 Patients must give informed consent.

- 5.1.3. Patients must agree to pre- and post- treatment biopsies.
- 5.1.4 Patients must have an ECOG performance status  $\leq 2$  (Appendix B).
- 5.1.5 Estimated life expectancy of at least 12 weeks.
- 5.1.6 Negative pregnancy test

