## 5.2 Exclusion Criteria

**A patient will not be eligible for this study if any of the following exclusion criteria are met.**

5.2.1 Second primary malignancy only if treatment would interfere with the patient's participation in this trial in the opinion of the treating physician. Clear exceptions are 1) patient had a second primary malignancy but has been treated and disease free for at least 3 years, 2) in situ carcinoma (e.g. in situ carcinoma of the cervix) and, 3) additional skin cancers that have been definitively treated by surgery and/or radiation. Patients with chronic lymphocytic leukemia will be allowed if their blood counts are within acceptable hematologic parameters and if they are not currently requiring cytotoxic or biologic anticancer treatment (supportive treatment such as IVIG is permitted).

5.2.2 Patients with distant organ metastases will not be included in this study.

5.2.3 Serious concomitant systemic disorders (including active infections) that would compromise the safety of the patient or compromise the patient's ability to complete the study, at the discretion of the investigator.

5.2.4 Age  $< 18$  years.

5.2.5 History of allergic reactions attributed to compounds of similar chemical or biologic composition to cetuximab or other agents used in the study.

5.2.6 Women who are pregnant, due to the teratogenic effects of radiation therapy and chemotherapy on the unborn fetus. Women of childbearing age must agree to undergo a pregnancy test prior to therapy and to use adequate contraception (hormonal or barrier method of birth control; abstinence) prior to study entry, for the duration of study participation and for 6 months after. Should a woman become pregnant or suspect she is pregnant while participating in this study, she should inform her treating physician immediately. Menopausal status is defined by one or more of the following:

Successful hysterectomy, bilateral tubal ligation or bilateral oophorectomy OR  
Amenorrhea  $\geq 12$  consecutive months without another cause or for women with irregular menstrual periods and taking hormone replacement therapy (HRT), a documented serum follicle stimulating hormone (FSH) level  $\geq 35$  mIU/mL

5.2.7 Presence of the following grade 3-4 electrolyte abnormalities (CTCAE, v. 4.0):

- Serum calcium (ionized or adjusted for albumin) < 8 mg/dl (1.75 mmol/L) or > 12.5 mg/dl (> 3.1 mmol/L) despite intervention to normalize levels

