- Magnesium < 1.4 mg/dl (< 0.4 mmol/L) or > 3 mg/dl (> 1.23 mmol/L) despite intervention to normalize levels
- Potassium < 3.5 mmol/L or > 6 mmol/L despite intervention to normalize levels

5.2.8 Prior radiation therapy is not an exclusion however, patient must have documented progression at the radiation site.

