## 6. Study Parameters

Evaluations	Pre-cetuximab	Weekly during neoadjuvant cetuximab	Post-cetuximab (Week 9)	At surgery or prior to RT 	30 days after surgery or XRT	Follow ups every 3 months after surgery or XRT for 2 years	After locoregional or distant failure
History, physical exam and tumor site assessment	X  (within 14 days of treatment)	X 	X 		X 	X 	X 
Photo of tumor and/or rash at head, neck, upper torso put into EMR	X (within 14 days of treatment)	X 	X 				
Incisional/core biopsy of primary tumor and loco-regional lymph nodes if involved	X  (within 30 days of treatment)			X  (any time during this interval)			X (within 30 days of relapse)
Biopsy of skin	X  (within 30 days of treatment)			X  (any time during this interval)			X (within 30 days of relapse)
CBC, differential, platelets	X (within 14 days of treatment)	X			X	X	
Serum Chemistries 	X (within 14 days of treatment)	X	X	X	X	X	
Liver Enzymes 	X (within 14 days of treatment)	X			X	X	
Pregnancy Test 	X (within 14 days of treatment)						

Radiographic Assessments 	X  (within 30 days of treatment)		X 			X	X 
---------------------------------------	---	--	----------------	--	--	---	----------------

\*A +/- 2 day window is allowed for all study assessments indicated on this trial except treatment for which a +/- 1 day window is allowed.

1. To include toxicity assessment, ECOG performance status, weight
2. Includes: Electrolytes, including serum magnesium, potassium, Calcium, BUN, Creatinine, Glucose,
3. Includes: Total and Direct. Bilirubin, AST/ALT, Alkaline Phosphatase, Albumin, Total Protein.
4. Women 18-55 who have not undergone menopause must have urine pregnancy test within 14 days of enrollment.
5. Tumor assessments as indicated by investigator, i.e. PET/CT, CT neck, chest/abdomen and pelvis or MRI of neck as needed to be obtained no more than 1 month prior to cetuximab; then per standard of care, in general, every three months after conclusion of surgery or XRT.
6. Every 7 days
7. Includes evaluation by surgery and radiation oncology for optimal local therapy. Surgery will assess optimal timing of rebiopsy during their evaluation of patient once neoadjuvant therapy is complete.
8. See section 11

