#### **7.4.3 Concomitant Medications**

There are no concomitant medications that are contraindicated with cetuximab.

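### Item 5.1.1 asks for untreated or relapsed disease but also admits residual disease after an investigational agent, so late shrinkage from that agent can be scored as a cetuximab response

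*Combined protocol and SAP*

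**What the plan says.** Item 5.1.1 (Section 5.1, Inclusion Criteria) opens with a mandatory condition: "Patients must have untreated or relapsed SCCS that is considered to be aggressive and locally advanced". The same item closes with a permission: "Patients may have had prior surgical interventions or been treated with investigational agents with residual or recurrent disease". No condition on disease course or time since treatment is attached to the investigational agents.

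For radiation the plan is stricter. Item 5.2.8 (Section 5.2, Exclusion Criteria) reads "Prior radiation therapy is not an exclusion however, patient must have documented progression at the radiation site". No section has a matching rule for prior drugs, and none gives a minimum interval since the last dose of one.

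Footnote 5 to the table in Section 6 sets the timing of baseline imaging: "to be obtained no more than 1 month prior to cetuximab". Section 7.2.3.1 compares the CT after 8 weeks of cetuximab with that pre-treatment CT, and a 30% fall in summed diameters is a partial response. Sections 15.1 and 15.2 test the resulting response rate against 10% in 20 patients.

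**The concern.** A tumor reduced but not cleared by an earlier drug is residual without having relapsed. The first sentence of 5.1.1 would turn that patient away, and the last sentence would admit the patient. Two people checking eligibility could decide differently, and neither would be misreading the text.

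The permissive reading matters because there is no control arm. Every qualifying reduction from baseline is credited to 8 weeks of cetuximab, and no step in the response assessment separates out an earlier agent. The baseline CT may be a month old, and nothing ties it to the end of the earlier treatment. It could therefore be taken while that treatment is still being given or still acting. Later shrinkage would then fall inside the cetuximab measurement window.

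The plan guards against this problem for radiation, where progression at the treated site is required. With only 20 patients, one or two misattributed responses could decide the primary test.

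**Working it through.** **Inputs from the protocol.** N = 20, null rate 10%, expected rate 30%, one-sided exact binomial test at 0.05, stated actual type I error 4.32% and power 76.2% (Sections 15.1 and 15.2).

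**Step 1: reproduce the plan's figures.** The success cut-off is not printed, so I looked for the one that gives the stated error. Here X is the number of responders among 20.

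| Success if X is at least | P at 10% | P at 30% |
|---|---|---|
| 4 | 13.30% | 89.3% |
| 5 | 4.32% | 76.2% |
| 6 | 1.13% | 58.4% |

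A cut-off of 5 or more reproduces both stated figures and is the implied rule.

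**Step 2: add carry-over patients.** The documents give neither the number k of such patients nor their chance q of being scored as responders. Both are assumptions here. The other 20 − k patients respond at the null rate of 10%.

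For k = 1:

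P(success) = q × P(Bin(19, 0.1) ≥ 4) + (1 − q) × P(Bin(19, 0.1) ≥ 5) = q × 0.1150 + (1 − q) × 0.0352

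- q = 0.2: 0.0230 + 0.0282 = 0.0512
- q = 0.3: 0.0345 + 0.0246 = 0.0591
- q = 0.5: 0.0575 + 0.0176 = 0.0751

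For k = 2:

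P(success) = q² × P(Bin(18, 0.1) ≥ 3) + 2q(1 − q) × P(Bin(18, 0.1) ≥ 4) + (1 − q)² × P(Bin(18, 0.1) ≥ 5) = q² × 0.2662 + 2q(1 − q) × 0.0982 + (1 − q)² × 0.0282

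- q = 0.2: 0.0106 + 0.0314 + 0.0180 = 0.0601 (from unrounded terms)
- q = 0.3: 0.0240 + 0.0412 + 0.0138 = 0.0790
- q = 0.5: 0.0666 + 0.0491 + 0.0070 = 0.1227

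| False-positive risk | q = 20% | q = 30% | q = 50% |
|---|---|---|---|
| No carry-over patient | 4.3% | 4.3% | 4.3% |
| One | 5.1% | 5.9% | 7.5% |
| Two | 6.0% | 7.9% | 12.3% |

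**Step 3: where the nominal level is crossed.** With one such patient, the risk passes 5% when q exceeds (0.0500 − 0.0352) / (0.1150 − 0.0352) = 0.0148 / 0.0798, about 19%. At q = 10% a carry-over patient is no different from the rest, and the risk stays at 4.3%.

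**The case against.** The strongest reply is that the opening sentence of 5.1.1 controls. It is mandatory, while the later sentence only permits. A tumor still shrinking on a recent agent is neither untreated nor relapsed, so such a patient would be ineligible. The word residual could also be meant for prior surgery, where it is ordinary and raises no drug carry-over. This reading is reasonable, but the text does not compel it. The later sentence covers surgery and investigational agents together and attaches residual or recurrent disease to both. The conflict is therefore real, and the protocol does not say which sentence prevails.

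The second reply concerns size. A false response needs at least a further 30% reduction after the baseline scan, from a drug already given. The prospective biochemotherapy study described in Section 2.1 had responses in 3 of 12 patients with regional nodal disease only (25%) under full treatment, so a 50% chance from leftover effect is high. Section 2.1 also stresses how few systemic options exist, so recent prior drug therapy may be uncommon. Both points stand. The lower end of the range deserves more weight, and the effect there is small.

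Three stronger readings are tempting, and the documents do not support them.

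- A reader might infer that concurrent cancer treatment is unlimited, since Section 7.4.3 says "There are no concomitant medications that are contraindicated with cetuximab". But Section 4.1 says "The patients will be under active treatment with cetuximab monotherapy for approximately 8 weeks", and item 5.2.1 lists as an exclusion "Second primary malignancy only if treatment would interfere with the patient's participation in this trial in the opinion of the treating physician". It also admits patients with chronic lymphocytic leukemia only "if they are not currently requiring cytotoxic or biologic anticancer treatment". What is missing is a general prohibition.
- A reader might infer that late toxicity of an earlier drug will be counted against cetuximab. Section 8 records causality for each adverse event entered on the case report form, and counts a preexisting condition only if it worsens. Attribution by the investigator is imperfect, but a safeguard exists.
- A reader might infer that admitting patients with prior anti-EGFR therapy is an error. No section makes it one. Resistance in such patients would lower the observed rate, which is conservative for this test. Whether to admit them is the sponsor's choice.

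**Conclusion.** The point holds as a defect in the eligibility wording. Item 5.1.1 contradicts itself on disease status after prior drug treatment, and nothing elsewhere resolves it for drugs as 5.2.8 does for radiation. Under the permissive reading, an uncontrolled comparison with a baseline CT up to a month old can credit another agent's effect to cetuximab.

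The size cannot be derived from the documents. The step 2 figures assume a true cetuximab rate at the null, one or two affected patients, and a carry-over response chance between 20% and 50%. They illustrate sensitivity and are not a forecast. At the low end, one such patient barely moves the error above its nominal level. If the strict reading is applied and no such patient enrolls, the stated 4.32% and 76.2% are unaffected. The wording should be corrected, but the point does not undermine the sample size or the test.

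**What to change.** Reconcile relapsed with residual in 5.1.1 by extending the logic of 5.2.8 to drugs. Possible wording: *Patients who have received systemic or investigational therapy for SCCS must have documented disease progression after that therapy, and the baseline CT must be performed after its last dose.* State separately that residual disease after surgery remains eligible, if that is the intent. Any minimum interval between the last dose and first cetuximab is for the sponsor to set, since the documents give no basis for a figure. Repeat the baseline CT condition in footnote 5 of Section 6 and on the eligibility checklist.

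This takes a short eligibility amendment and matching checklist lines. The sample size, cut-off and analysis do not change. The downside is small: a few patients would be excluded, would start later, or would need a new baseline scan.

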## 5.2 Exclusion Criteria

**A patient will not be eligible for this study if any of the following exclusion criteria are met.**

5.2.1 Second primary malignancy only if treatment would interfere with the patient's participation in this trial in the opinion of the treating physician. Clear exceptions are 1) patient had a second primary malignancy but has been treated and disease free for at least 3 years, 2) in situ carcinoma (e.g. in situ carcinoma of the cervix) and, 3) additional skin cancers that have been definitively treated by surgery and/or radiation. Patients with chronic lymphocytic leukemia will be allowed if their blood counts are within acceptable hematologic parameters and if they are not currently requiring cytotoxic or biologic anticancer treatment (supportive treatment such as IVIG is permitted).

5.2.2 Patients with distant organ metastases will not be included in this study.

5.2.3 Serious concomitant systemic disorders (including active infections) that would compromise the safety of the patient or compromise the patient's ability to complete the study, at the discretion of the investigator.

5.2.4 Age  $< 18$  years.

5.2.5 History of allergic reactions attributed to compounds of similar chemical or biologic composition to cetuximab or other agents used in the study.

5.2.6 Women who are pregnant, due to the teratogenic effects of radiation therapy and chemotherapy on the unborn fetus. Women of childbearing age must agree to undergo a pregnancy test prior to therapy and to use adequate contraception (hormonal or barrier method of birth control; abstinence) prior to study entry, for the duration of study participation and for 6 months after. Should a woman become pregnant or suspect she is pregnant while participating in this study, she should inform her treating physician immediately. Menopausal status is defined by one or more of the following:

Successful hysterectomy, bilateral tubal ligation or bilateral oophorectomy OR  
Amenorrhea  $\geq 12$  consecutive months without another cause or for women with irregular menstrual periods and taking hormone replacement therapy (HRT), a documented serum follicle stimulating hormone (FSH) level  $\geq 35$  mIU/mL

5.2.7 Presence of the following grade 3-4 electrolyte abnormalities (CTCAE, v. 4.0):

- Serum calcium (ionized or adjusted for albumin) < 8 mg/dl (1.75 mmol/L) or > 12.5 mg/dl (> 3.1 mmol/L) despite intervention to normalize levels
- Magnesium < 1.4 mg/dl (< 0.4 mmol/L) or > 3 mg/dl (> 1.23 mmol/L) despite intervention to normalize levels
- Potassium < 3.5 mmol/L or > 6 mmol/L despite intervention to normalize levels

5.2.8 Prior radiation therapy is not an exclusion however, patient must have documented progression at the radiation site.

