### **5.6 Study Enrollment Procedures**

A copy of the institution's IRB-approved informed consent document and written justification for any changes made to the informed consent for this protocol must be on file at the Rutgers Cancer Institute of New Jersey's Office of Human Research Services (OHRs) before any participating institution may enter patients. The CINJOG institution consent form must be reviewed and approved by OHRs Regulatory Affairs and all documents must be received (i.e., IRB approved documentation, IRB approved consent form, etc.).

To register eligible patients on this study, each site will contact OHRs. Contact information will be provided at the time of site activation. The signed and dated eligibility checklist, completed signature page of the consent form and additional source documents if requested by OHRs will need to be provided. Once OHRs verifies eligibility, a unique patient study number will be issued. The patient will not be identified by name. This is the point that the patient is considered on study. Patients must not start protocol treatment prior to registration.

If a patient does not receive any protocol therapy, baseline data will be collected and submitted on the pre-study and follow-up electronic case report forms (eCRF). The reason for not starting protocol therapy will be documented in the "follow-up eCRF". Case report form completion instructions and training will be provided to each participating institution prior to study activation at the participating institution.

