### 7.3.3.2 Infusion Reactions

Serious infusion reactions occurred with the administration of Cetuximab in approximately 3% of patients in clinical trials, with fatal outcome reported in less than 1 in 1000. Reduce the infusion rate by 50% for NCI CTCAE Grade 1 or 2 and non-serious NCI CTCAE Grades 3–4 infusion reactions. Once the infusion rate has been decreased due to an infusion reaction, it will remain decreased for all subsequent infusions. If the subject has a second infusion reaction at the slower infusion rate, the infusion should be stopped, and the subject should receive no further cetuximab treatment. Immediately and permanently discontinue cetuximab for serious infusion reactions that are life threatening and/or require hospitalization. All patients will be premedicated with diphenhydramine hydrochloride, 50 mg, (or an equivalent antihistamine) by *i.v.* 30-60 minutes prior to the first dose of cetuximab in an effort to prevent an infusion reaction. At the discretion of the treating physician, dexamethasone, 20 mg, and an H2 blocker also may be administered.

Serious infusion reactions, requiring immediate, permanent discontinuation of cetuximab included rapid onset of airway obstruction (bronchospasm, stridor, hoarseness), hypotension, shock, loss of consciousness, myocardial infarction, and/or cardiac arrest. Severe (NCI CTCAE Grades 3 and 4) infusion reactions occurred in 2–5% of 1373 patients in clinical trials, with fatal outcome in 1 patient. Approximately 90% of severe infusion reactions occurred with the first infusion despite premedication with antihistamines.

Monitor patients for 1 hour following Cetuximab infusions in a setting with resuscitation equipment and other agents necessary to treat anaphylaxis (eg, epinephrine, corticosteroids, intravenous antihistamines, bronchodilators, and oxygen). Monitor longer to confirm resolution of the event in patients requiring treatment for infusion reactions. Immediately and permanently discontinue Cetuximab in patients with serious infusion reactions.

Infusion reactions may be managed per the following table:

Adverse Event Grade	Treatment Guidelines

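### Two rules cannot be applied as written: the lower calcium and magnesium entry limits in 5.2.7 differ by unit, and non-serious Grade 3 infusion reactions have two opposite instructions.

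*Combined protocol and SAP*

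**What the plan says.** **Entry limits.** Section 5.2.7 introduces its list as "Presence of the following grade 3-4 electrolyte abnormalities (CTCAE, v. 4.0"). The calcium item reads "Serum calcium (ionized or adjusted for albumin) < 8 mg/dl (1.75 mmol/L) or > 12.5 mg/dl (> 3.1 mmol/L") and the magnesium item reads "Magnesium < 1.4 mg/dl (< 0.4 mmol/L) or > 3 mg/dl (> 1.23 mmol/L) despite intervention to normalize levels". Each limit is given in mg/dl with mmol/L in brackets. Section 5.6 adds a central check: "Once OHRs verifies eligibility, a unique patient study number will be issued".

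**Infusion reactions.** The running text of 7.3.3.2 says: "Reduce the infusion rate by 50% for NCI CTCAE Grade 1 or 2 and non-serious NCI CTCAE Grades 3–4 infusion reactions". Section 12.2 repeats this rule. The text reserves stopping for serious events: "Immediately and permanently discontinue cetuximab for serious infusion reactions that are life threatening and/or require hospitalization". It then lists examples: "Serious infusion reactions, requiring immediate, permanent discontinuation of cetuximab included rapid onset of airway obstruction (bronchospasm, stridor, hoarseness), hypotension, shock", among others. The management table later in 7.3.3.2 has a Grade 3 row covering symptomatic bronchospasm, need for parenteral medication, allergic edema or angioedema, and hypotension. Its instruction is immediate interruption and permanent discontinuation, with no exception for non-serious events. The sentence that introduces the table is permissive.

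**The concern.** An eligibility limit printed in two units is one limit only if the two figures agree. Where they do not, the same blood result can be read as eligible or ineligible, and neither reading breaks the protocol as printed. Section 7.3.4.5 reports hypomagnesemia in 55% of patients on cetuximab, severe in 6–17%, so the starting magnesium is not an idle detail for this drug.

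The infusion-reaction rules tell the treating physician to do opposite things. A patient with a Grade 3 reaction that is not serious is either re-treated at half rate or never treated again. Safety and feasibility form a co-primary objective in section 1.1, and section 16.5 rests the risk-benefit case partly on patient selection and stopping criteria. Both rules belong to those protections.

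**Working it through.** **Plan's own statistical figure.** Section 15.2 gives 20 patients, 10% against 30%, and a one-sided exact binomial test. Success at 5 or more responses of 20 gives a type I error of 0.0432 and power of 0.7625, which reproduces the stated 4.32% and 76.2%. Nothing below changes these.

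**Unit conversion.** mmol/L = mg/dl × 10 ÷ atomic mass. The atomic masses are standard constants (calcium 40.078, magnesium 24.305). The printed limits come from 5.2.7.

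| Limit | mg/dl | Converted (mmol/L) | Printed (mmol/L) | Difference |
|---|---|---|---|---|
| Calcium, upper | 12.5 | 125 ÷ 40.078 = 3.12 | 3.1 | −0.6% |
| Calcium, lower | 8 | 80 ÷ 40.078 = 1.996 | 1.75 | −12.3% |
| Magnesium, upper | 3 | 30 ÷ 24.305 = 1.234 | 1.23 | −0.3% |
| Magnesium, lower | 1.4 | 14 ÷ 24.305 = 0.576 | 0.4 | −30.6% |

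The upper limits agree to rounding; the lower limits do not.

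The plan's own ratios show the same without any outside constant. In mg/dl per mmol/L:
- Calcium: 12.5 ÷ 3.1 = 4.03 (upper) against 8 ÷ 1.75 = 4.57 (lower).
- Magnesium: 3 ÷ 1.23 = 2.44 (upper) against 1.4 ÷ 0.4 = 3.50 (lower).

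**Disputed ranges.** Converting the printed mmol/L figures back:
- Calcium: 1.75 × 40.078 ÷ 10 = 7.01 mg/dl. Values of 7.0 to 8.0 mg/dl (1.75 to 2.00 mmol/L) are classed both ways.
- Magnesium: 0.4 × 24.305 ÷ 10 = 0.97 mg/dl. Values of 0.97 to 1.4 mg/dl (0.40 to 0.58 mmol/L) are classed both ways.

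The calcium line also gives one figure for two different measurements, ionized and albumin-adjusted calcium.

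**Infusion reactions, side by side.**

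| Reaction | 7.3.3.2 text and 12.2 | 7.3.3.2 table |
|---|---|---|
| Grade 1–2 | Halve rate, continue | Halve rate, continue (worded for delayed drug fever) |
| Grade 3, serious (e.g. bronchospasm with rapid airway obstruction, hypotension) | Stop permanently | Stop permanently |
| Grade 3, not serious (e.g. parenteral medication needed, or allergic edema, without airway obstruction, life threat or hospitalization) | Halve rate, continue | Stop permanently |
| Life-threatening | Stop permanently | Stop permanently |

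Only the third row conflicts.

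**Size of that row.** Section 7.3.3.2 gives serious reactions in about 3% and severe (Grade 3 and 4) reactions in 2–5%. Assume serious reactions are a subset of severe ones and that the two rates come from comparable patients. The non-serious severe share is then at most 5% − 3% = 2%. At the lower end the difference is negative and is set to 0. For 20 patients:
- Expected number: 20 × 0% = 0 to 20 × 2% = 0.4.
- Chance of at least one: 0 to 1 − 0.98^20 = 33%.

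**The case against.** **Entry limits.** Section 3 names one institution on two campuses, and mg/dl is printed first. If its laboratory reports mg/dl, staff may apply that figure throughout and never meet the conflict. That is plausible, but reporting units are not stated. The limits bind only after attempts at correction, and eligibility is verified centrally. Both facts narrow the reach, but neither says which figure governs. A reader might infer that one figure is plainly the misprint. The documents do not support that: the answer depends on CTCAE v4.0, which is not reproduced for these electrolytes.

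**Infusion reactions.** The table is introduced permissively, and the text has safeguards after re-treatment: the slower rate is kept, patients are observed for 1 hour, and "If the subject has a second infusion reaction at the slower infusion rate, the infusion should be stopped", with no further cetuximab. These limit harm once re-treatment is chosen; they do not choose it. The table's Grade 3 row itself is mandatory in wording. A stronger point is that section 8.2 counts important medical events as serious, with intensive treatment for allergic bronchospasm as an example. Read that way, still more Grade 3 reactions stop drug under both rules. This shrinks the disputed group but does not empty it.

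A reader might take the chance of at least one severe reaction in 20 patients, 1 − 0.98^20 = 33% to 1 − 0.95^20 = 64%, as the exposure. That range covers all severe reactions, including the serious ones on which both rules agree.

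**Rash grading.** A reader might also infer that weekly folliculitis grading is unworkable, because 9.1 cites 7.3.3.1, where the acneiform row prints the same text for Grades 1 and 2 and has no Grade 4. That goes too far. Section 9.1 cites the section's criteria as a whole. The rash/desquamation row in that table separates Grade 1 from Grade 2 and has a Grade 4. The remark about a Grade 2 threshold describes previous reports and is not a trial rule. The Grade 3/4 dose rule sits beside the 7.3.3.3 table and reads naturally with it. Folliculitis is not an outcome in 15.4. What remains is an editorial mismatch.

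**Conclusion.** Both faults stand and should be corrected. The lower limits in 5.2.7 are wrong as printed, by 12% for calcium and 31% for magnesium when the mmol/L figure is compared with its mg/dl partner. This rests on unit conversion alone. How many candidates would fall in the disputed ranges is not given.

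The infusion-reaction conflict is real but confined to Grade 3 reactions that are not otherwise serious. The 0 to 2% estimate is rough: it depends on the subset assumption and on two quoted rates that may come from different pooled data. The plausible impact is at most a patient or so, but for that patient the two instructions are opposite.

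These are wording errors in eligibility and safety handling. They do not touch the sample size, the power or the primary test.

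**What to change.** 1. **Section 5.2.7.** Print one matching pair of lower limits, chosen by the sponsor against the CTCAE v4.0 grade 3–4 that the criterion names:
   - calcium < 8 mg/dl (< 2.0 mmol/L) and magnesium < 1.4 mg/dl (< 0.58 mmol/L); or
   - calcium < 7.0 mg/dl (< 1.75 mmol/L) and magnesium < 0.97 mg/dl (< 0.4 mmol/L).

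   State that the calcium limit is for albumin-adjusted calcium, or give a separate ionized limit.

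2. **Section 7.3.3.2 text, its table, and 12.2.** State one action for Grade 3 reactions. The conservative choice is to halve the rate for Grade 1–2 only and discontinue permanently for Grade 3–4. The need is for consistency; the other choice is open to the sponsor if the table is changed to match.

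3. **Editorial only.** The two tables labelled CTCAE 4.0 in 7.3.3.1 and 7.3.3.3 differ in their acneiform, pruritus and nail rows, so 9.1 and the Grade 3/4 dose rule should both cite the 7.3.3.3 table. Section 7.2.2 should refer to the severe-rash exception. The pointer to 7.4.5.1 should be 7.3.6.1.

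**Cost.** A short wording amendment, with no added visits, procedures or patients. If the higher entry limits are kept, candidates below them can still be repleted and re-tested. The conservative infusion rule may stop a few patients who could have been re-treated.
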